4.0 STUDY DESIGN

The study is designed as a non-randomized, Phase II study of aerosolized cyclosporine A in solution with propylene glycol (CIS) in hematopoietic stem cell transplant recipients at least 99 days post transplant (Group A) or lung transplant recipients at least 6 months post transplant (Group B) who have been diagnosed with biopsy proven bronchiolitis obliterans or Bronchiolitis Obliterans Syndrome. The *primary endpoint* of each study group is FEV₁ improvement or stabilization from study baseline at week 18 for two successive measures, at least 1 week apart, no more than two weeks apart. Subjects who cannot tolerate the medication (at least 150mg dose), have disease progression (beginning at week 9) as defined by a 20% or more decline in FEV₁ on two successive measurements at least 2 weeks apart or require >25% increase in one or more existing immunosuppressive agents or the addition of new systemic immunosuppressive therapies due to worsening symptoms related to BOS will go off study. As of Amendment M, lung transplant patients are no longer being enrolled on this protocol.

* Based on two successive measures at least two weeks apart,

beginning at week 9

11-H-0068 PI: [name]

Version 16 (Amendment N) July 22, 2019

13

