Any subject that demonstrates disease progression (beginning at week 9) as defined by a 20% or more decline in FEV_1 on two successive measurements at least 2 weeks apart, or >25% increase in existing or addition of new immunosuppressive therapies (sustained for 3 weeks, excluding adjustments made for target drug levels), above baseline levels, due to worsening symptoms related to BOS, will be categorized as a treatment failure and will discontinue study drug administration and proceed with end of study drug assessment. For all others, study drug administration will end at week 19 assessment.

Deviation plan for a missed dose: Subjects will be treated with CIS three times weekly ideally on Monday, Wednesday, and Friday of the week. Should a subject miss a scheduled dose of CIS, we will attempt to alter the dosing regimen for that week so that the subject will still receive three doses of CIS over a week with a limit of 1 dose per day. Data will be captured and reported for subjects who deviate from the treatment plan.

Medication Holds: During study participation, subjects may be instructed to hold administration of CIS after development of an adverse event or other reason at the discretion of the PI. Information pertaining to the reason for and the duration of the medication hold will be captured in the subjects' medical record. If study drug is held for more than 7 days, the time of the hold will not be counted towards the overall study week count. Study drug can be held for up to 12 weeks.

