6.2.3 Permitted Concomitant Medications

Post Transplant Medications: Subjects that require an increase in existing immunosuppressive meds by 25% due to worsening BOS symptoms (sustained for 3 weeks, excluding adjustments made for target drug levels) or need addition of new immunosuppressive therapies (sustained for 3 weeks), above baseline levels, due to worsening lung disease or BOS symptoms after week 9 will be categorized as treatment failures. However, if the increase or addition of new immunosuppressive therapies is for GVHD not involving the lung or to maintain baseline drug levels, this data will be captured and the subject will continue on study. Efforts will be made to make no changes in existing medical therapies other than tapering immunosuppressants in subjects who have PFTs showing stable or improved pulmonary function.

Systemic immunosuppressants will be tapered beginning at week 6, if subjects have an improvement or stabilization of FEV_1 compared to study baseline values, at the discretion of the PI, taking into account the subject's other manifestations of GVHD. Attempts will be made to taper prednisone first, before other systemic immunosuppressants. Prednisone will be decreased by 25% at the first taper. Subsequent tapers will be at the discretion of the PI. Lung transplant recipients will not have systemic immunosuppressants tapered.

Subjects that have improvement or stabilization of FEV_1 , are not on prednisone, and are only on calcineurin inhibitors, will have their steady state calcineurin inhibitor (systemic cyclosporine or tacrolimus) dose tapered at the discretion of the PI. The calcineurin inhibitor dose will be decreased by 25% at the first taper. Subsequent tapers will be at the discretion of the PI.

Lung Infection Prophylaxis:

Lung infection prophylaxis will be at the discretion of the PI, taking into account the patient's other concomitant medications and medical history. The following are guidelines:

- For PCP pneumonia prophylaxis, subjects will take Bactrim, one double strength tablet (800/160mg) orally three times weekly or aerosolized pentamidine 300mg every four weeks by inhalation.
- For antiviral prophylaxis, subjects will receive acyclovir 800 mg twice daily. Pediatric subjects less than 40kgs will receive acyclovir 20mg/kg po twice daily to a maximum dose of 800mg twice daily.

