3) subjects who require increases in existing or addition of new immunosuppressive therapies due to worsening symptoms related to BOS (sustained for 3 weeks, excluding adjustments made for target drug levels) after week 9

4) subjects with BO or BOS who had stable disease (active BOS, stable by FEV_1 criteria) at study entry and are deemed to have a stable FEV_1 , increase < 10% and decrease < 10% at the end of study, with less than a 25% reduction in one or more systemic immunosuppressive medications (sustained for 3 weeks, excluding adjustments made for target drug levels) while receiving CIS. 5) subjects that aren't able to tolerate the 150mg dose for more than two weeks.

All subjects who begin treatment will be included in the primary analysis, except those subjects that are unable to tolerate the 150mg dose for at least two weeks. In order to maintain an adequate sample size, additional subjects will be offered enrollment in order to account for those subjects that were unable to tolerate the 150mg dose for at least two weeks.

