10.5 Off Study Criteria

10.5.1 Subject choice: Subjects may withdraw from the study at their request any time. The risks of withdrawing will be discussed, as will alternative treatment options. Those subjects who choose to withdraw will be strongly encouraged to participate in study assessments until he/she initiates alternative BO therapy. In this scenario, patients will be deemed off study-drug, but have the option to continue on-study.

10.5.2 Principal investigator decision:

Subjects will be taken off study drug during the 18 week period of intervention if they:

- Have disease progression (beginning at week 9) as defined by a 20% or more decline in FEV₁ on two successive measurements at least 2 weeks apart
- Have evidence of an NCI grade IV toxicity related to study drug administration

- Require >25% increase in one or more existing immunosuppressive agents or the addition of new systemic immunosuppressive therapies due to worsening symptoms related to BOS (sustained for 3 weeks, excluding adjustments made for target drug levels) after week 9 (see section 6.2.3).
- Develop worsening performance status, defined by ECOG score ≥ 3 (please see hematology supportive care guidelines)
- Develop disease relapse or a significant non-pulmonary transplant complication in which death is likely to occur prior to the conclusion of the 18 week study period
- Are unable to comply with the study visits or become severely ill and cannot comply with the intervention.
- Are unable to tolerate the 150mg dose of the inhaled CsA
- Develop severe pulmonary infection that fails to respond to conventional treatment or where no effective drug treatment exists
- Subject becomes pregnant

Subjects that have stopped study drug administration will be asked to complete the study assessments, as off-study drug participants, whenever feasible. Lung deposition studies and pharmacokinetic tests will not be performed in off-study drug participants. Chest CT and bronchoscopy will only be performed if clinically indicated. If off-study drug subjects are unable or unwilling to complete the study assessments, they will be referred back to their primary transplant team and will end study participation.

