10.5.3 Completion of the study

Upon completion of the week 19 assessment, subjects will have completed study participation and be taken off study and referred back to their primary transplant team to continue post transplant monitoring and care. After Week 19 assessment is completed, subjects with stabilized or improved disease will be offered the option of continuing CsA on **an extended access protocol**.

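### The plan's sections conflict on how rescue immunosuppression for worsening BOS is scored, and on the wording of 10.2, 6.2.3 and 10.5.2 a response obtained under rescue can be credited to CIS

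*Combined protocol and SAP*

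**What the plan says.** Five places in the combined protocol and SAP deal with systemic immunosuppression that is added or increased because BOS worsens.

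- **10.2, failure item 3:** failure if "sustained for 3 weeks, excluding adjustments made for target drug levels) after week 9". No size threshold is given.
- **6.2.3:** an increase of 25%, or a new agent, each sustained for 3 weeks, "due to worsening lung disease or BOS symptoms after week 9 will be categorized as treatment failures".
- **10.5.2:** an increase above 25%, or a new agent, "sustained for 3 weeks, excluding adjustments made for target drug levels) after week 9 (see section 6.2.3"). The consequence is coming off study drug, with assessments continuing where feasible.
- **6.2.1:** ">25% increase in existing or addition of new immunosuppressive therapies (sustained for 3 weeks, excluding adjustments made for target drug levels), above baseline levels" is a treatment failure. The week-9 limit stands beside the FEV1 criterion, so it is unclear whether it also governs rescue.
- **4.0:** subjects who need an increase above 25%, or a new agent, "due to worsening symptoms related to BOS will go off study". There is no 3-week condition, and the week-9 limit is again attached to the FEV1 criterion.

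Section 10.3 scores a subject who leaves the study before the endpoint is evaluated as a non-responder. The endpoint in 10.1 is the average of the week-18 and confirmatory FEV1. The 10.1 table does not consider immunosuppression for progressive entrants (stabilized or improved) or for stable entrants who improve by 10% or more. Stable entrants with flat FEV1 need a reduction of at least 25% in one or more drugs. Under 6.2.1, "study drug administration will end at week 19 assessment", and 10.5.3 adds: "Upon completion of the week 19 assessment, subjects will have completed study participation and be taken off study".

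**The concern.** The trial has no control arm, so the responder count is the whole of the efficacy evidence. Section 2.5 puts improvement or stabilization on conventional immunosuppression at 10-60% of patients. A subject whose lung function is held by added systemic treatment can thus look the same as one helped by CIS. If the scoring rule misses some of that treatment, the missed cases can only add to the responder count.

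Section 6.2.4 recognises that added immunosuppression can compromise the primary endpoint. However, the tracking it provides is for GVHD outside the lung. Rescue for the lung itself depends on the rules listed above, and they do not agree.

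**Working it through.** **1. One subject under each section.** Take a progressive entrant who worsens by less than 20%, starts a new systemic agent for BOS in week 4, stays on it, and has flat FEV1 at week 18 and at confirmation.

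| Section | Result |
|---|---|
| 10.2 item 1 (decline above 20%) | not triggered |
| 10.2 item 3, 6.2.3, 10.5.2, if the rescue must start after week 9 | not a failure; the 10.1 table gives stabilization, so a responder |
| 10.2 item 3, if rescue still in force after week 9 counts | failure |
| 6.2.1, week-9 limit read as covering FEV1 only | failure |
| 4.0 with 10.3 | off study, so a non-responder |

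**2. Late rescue.** A start in the last 3 weeks cannot complete 3 sustained weeks by the week-19 exit. No section says how that is scored. Rescue begun after the week-18 test can affect only one of the two averaged FEV1 values, and rescue after the confirmatory test affects neither.

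**3. Share of start weeks left uncounted.**

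- Rule applies after week 9: 9 + 3 = 12 of 19 (63%).
- Rule applies from the start of week 9: 8 + 3 = 11 of 19 (58%).
- No week-9 limit on rescue, 3-week condition kept: 3 of 19 (16%).
- 4.0 alone: 0 of 19.

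These are counts of possible start weeks, not shares of patients.

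**4. The plan's design reproduced.** Inputs from 10.2: null 0.30, alternative 0.50, stop at 6 or fewer of 19, success at 17 or more of 39. With R the number of responders required,

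P(success) = Σ (x = 7 to 19) P(X₁ = x) × P(X₂ ≥ R − x), where X₁ ~ Bin(19, p) and X₂ ~ Bin(20, p).

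For R = 17 this gives 0.0455 at p = 0.30 and 0.804 at p = 0.50, which agrees with the stated alpha of 0.05 and 80% power. A search over two-stage designs returns 39 as the smallest feasible maximum.

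Section 10.2 also tests the null by asking whether the lower 95% confidence limit exceeds 0.3. The exact two-sided lower limit is 0.278 for 17/39 and 0.301 for 18/39, so that test needs R = 18.

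**5. Illustration of the effect.** The true CIS response is 30%, and an assumed number of percentage points of rescue-assisted response is counted in addition.

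| Points added | Counted p | R = 17 | R = 18 |
|---|---|---|---|
| 0 | 0.300 | 4.6% | 2.3% |
| 2.5 | 0.325 | 8.9% | 5.0% |
| 5 | 0.350 | 15.6% | 9.5% |
| 10 | 0.400 | 35.6% | 25.5% |

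Five points is 0.05 × 39 = 1.95, about two subjects.

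**6. How much rescue that needs.** With the 10-60% range from 2.5 as the chance of responding on rescue, 5 points requires between 5/0.60 = 8.3% and 5/0.10 = 50% of subjects to be rescued in an uncounted period. Ten points requires 16.7% to 100%. The documents give no rescue rate against which to judge this.

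**The case against.** A reader might infer that rescue counts only if it starts after week 9, so that 12 of the 19 weeks escape scoring. The documents do not support that as a settled rule.

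- Item 3 does not use the word start. It can be read to catch rescue begun early and still required for 3 weeks after week 9.
- Sections 4.0 and 6.2.1 allow readings on which the uncounted period is 0 or 3 weeks.
- Item 1 fails any subject whose FEV1 declines by more than 20% during the 18 weeks, with no week-9 limit, so only smaller declines are at issue.
- Stable entrants with flat FEV1 are largely protected by the required 25% reduction.
- The late gap is inferred from silence.

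All of this stands, and it narrows the point. It does not remove it: the favourable readings are not stated, and 10.5.2 refers to coming off study drug rather than off study, so the non-responder clause in 10.3 need not apply. The stratified analyses for immunosuppression in 10.3 are unspecified and would not alter the count compared with 17 of 39.

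It can also be said that changing the primary endpoint of an open single-arm trial late in its life has a price of its own. That is a fair argument for reconciling the existing text and adding a sensitivity analysis, rather than writing a new criterion.

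**Conclusion.** The point holds as a contradiction in endpoint scoring. On the wording of 10.2 item 3, 6.2.3 and 10.5.2, a progressive entrant, or a stable entrant who improves by 10% or more, can be counted as a CIS responder after BOS-driven rescue begun before week 9. Section 4.0 with 10.3 makes the same subject a non-responder. How late rescue is scored is not stated.

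The size cannot be fixed. The affected share of start weeks is 12, 11, 3 or 0 of 19 depending on the reading, and the rescue rate is unknown. The rise from 4.6% to 15.6% (or from 2.3% to 9.5%) rests on an assumed 5 points of misattributed response and should not be read as an estimate. A reader might infer from it that the trial's error rate is in fact inflated threefold; the documents do not show that. Because the conflict decides who is a responder in an uncontrolled primary test, it should be settled before the analysis.

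**What to change.** 1. Reconcile 4.0, 6.2.1, 6.2.3, 10.2 item 3, 10.5.2 and the 10.1 table into one endpoint-scoring rule, kept separate from the rule for stopping study drug. It should state how BOS-driven rescue before week 9 is scored, including rescue begun early and still in force later, and how a 3-week period that is incomplete at the week-18 or confirmatory PFT is scored. The differing size thresholds (none in 10.2, 25% in 6.2.3, above 25% elsewhere) should be settled in the same edit.
2. Pre-specify a sensitivity analysis of the primary endpoint in which any new or increased systemic immunosuppression for BOS, from first CIS dose to the confirmatory PFT, counts as non-response. Report both response rates.

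No clinical management or study-drug stopping rule is proposed here; which of the conflicting clinical rules applies is for the investigators to decide.

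The cost is wording in those sections and one further tabulation. Concomitant medications are already reviewed at screening, at the end of week 1 and at weeks 6, 9, 12, 15 and 18. The visit lists in 7.10 and 7.11.1 do not show a review at week 19, so one line may be needed there. The reported response rate may be slightly lower.

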10.3 Data Analyses

All subjects who begin treatment will be included in the primary analyses, except those subjects that are unable to tolerate the 150mg dose for at least two weeks. The subject who goes off study before the time when the primary endpoint is evaluated will be considered as a non-responder. Every effort will be made to reach and evaluate the subjects at the 6 week, 9 week, 12 week, 15 week, 18, and 19 week end of intervention period. Adverse events will be tabulated by severity and disease (lung versus hematopoietic). For secondary endpoints, especially, the endpoints that were measured at multiple times such as 6, 9, 12, 15, 18, 19 weeks or until study end, a mixed-effects regression approach will be used to estimate the change of the endpoints and the effect of prognostic factors.

Final statistical analysis will be performed once all subjects have completed the end of study assessments and all data have been archived for analysis. We will use stratified analyses to account for effects of systemic immunosuppressive agents and other prognostic factors.

Secondary endpoints (such as change of 6 minute walk and the quality of life, etc) will be studies by repeated measured mixed effects regression, multiple regression, logistic regression and nonparametric regression models, if deemed appropriate.

Pharmacokinetic analysis

Inhaled cyclosporine pharmacokinetics will be determined by non-compartmental or compartmental analysis using WINNOLIN (Pharsight, Mountain View, CA) or other software as appropriate. For subjects who are administered both oral and inhaled cyclosporine, concentrations will be analyzed using the superposition principle. Parameters estimated will include but not limited to eliminate rate constant, volume of distribution, and area under the concentration versus time curve.

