10.2 Sample size

For each study group, we determine the sample size using the Two-Stage Minimax Design of Simon $(1989)^{20}$. We test the null hypothesis that the proportion of subjects that respond to therapy (improvement or stabilization) is 0.3 or less against the alternative hypothesis that the proportion of subjects that respond to therapy (improvement or stabilization) is 0.5 or more. With alpha = 0.05and 80% power, a maximum of 39 subjects will be needed for each of study groups A and B. In each study group, at the first stage, up to 19 subjects will be accrued and if 6 or fewer subjects have a response to CIS at 18 weeks, we will conclude that the treatment is not effective and we will stop that study group. Note that all 19 subjects may not need to be accrued, as long as 13 subjects do not show improvement or stabilization. If 7 or more of the 19 subjects respond to therapy at 18 weeks at the first stage in one of the study groups, then an additional 20 subjects will be accrued, bringing the total number of subjects to a maximum of 39. If the total number of subjects responding is 16 or fewer, we conclude that the treatment is not effective. If at least 17 of 39 subjects respond we will consider this treatment successful. Once again, this may happen before all 39 subjects are accrued. A 95% confidence interval for the proportion of subjects improving or stabilizing will be given. Based on the sample size of the study, the two-sided confidence interval will be obtained with the binomial exact method or the normal approximation, if appropriate. We will test our null hypothesis (that the proportion of response is 0.3 or less) formally using the confidence interval approach. If the lower 95% limit of the confidence interval is greater than 0.3, we will conclude the null hypothesis is rejected and the study treatment is successful. If the lower 95% limit of the confidence is less than 0.3, we will not reject the null hypothesis.

Subjects who are unable to tolerate a dose escalation to 300 mg but are able to tolerate 150 mg inhalation for at least two weeks will be included in the primary analysis. Subjects who will be considered treatment failures include:

1) those who develop progression of baseline BO (>20% decline in FEV1) during the 18 week course of the study

2) those who are deemed to have progressed at the end of study as evidenced by an FEV1 decline $\geq 10\%$

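### Subjects who stop CIS for reasons outside the 10.2 failure list but stay on study have no outcome rule, so some can be scored as responders to CIS

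*Combined protocol and SAP*

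**What the plan says.** Section 10.3 handles early exit with one sentence, tied to leaving the study: "The subject who goes off study before the time when the primary endpoint is evaluated will be considered as a non-responder".

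Section 10.5 treats stopping drug and leaving the study as separate events. Under 10.5.1, for subjects who withdraw by choice, "patients will be deemed off study-drug, but have the option to continue on-study". Under 10.5.2, for stops decided by the investigator, "Subjects that have stopped study drug administration will be asked to complete the study assessments, as off-study drug participants, whenever feasible".

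Section 4.0 uses different language. Subjects who cannot tolerate at least 150 mg, who progress, or who need more immunosuppression "due to worsening symptoms related to BOS will go off study".

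Section 10.2 adds five kinds of treatment failure, none of which depends on leaving the study:

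1. FEV1 progression of more than 20% during the 18 weeks.
2. An end-of-study decline of 10% or more.
3. Increased or new immunosuppression for worsening BOS after week 9.
4. Stable disease at entry and stable FEV1 at the end, without a 25% immunosuppressant reduction.
5. Inability to tolerate 150 mg for more than two weeks.

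Sections 6.2.1 and 6.2.3 also class progression and escalation for BOS as treatment failure. The first-stage rule in 10.2 is worded as a count of responses to the drug: "up to 19 subjects will be accrued and if 6 or fewer subjects have a response to CIS at 18 weeks".

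**The concern.** A subject who has stopped CIS but still attends is not off study, so the 10.3 sentence does not reach that subject. If the reason for stopping is also absent from the 10.2 list, the only remaining rules are the FEV1 criteria in 10.1. For a subject with progressive disease at entry, these ask only whether FEV1 is within 10% of baseline or better, and the response table marks immunosuppression as not applicable. A patient removed for grade IV toxicity caused by CIS could therefore be counted as a success for CIS.

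The trial has no control arm, and each group is judged by a fixed count. Any off-drug subject scored as a responder moves that count towards success. It also leaves the analyst a choice that should be settled before the data are seen.

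**Working it through.** **Which stopping reasons have an outcome rule.** Setting the 10.5 reasons for stopping drug against 10.2:

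| Reason for stopping CIS (10.5) | Outcome rule if the subject stays on study |
|---|---|
| FEV1 decline of 20% or more | Progression failure in 10.2 and 6.2.1 |
| More immunosuppression for BOS after week 9 | Failure, 10.2 item 3 |
| Intolerance of 150 mg within two weeks | Addressed in 10.2 and 10.3 (item 5; excluded and replaced) |
| Intolerance first appearing after two weeks | None |
| Drug-related grade IV toxicity | None |
| ECOG 3 or worse | None |
| Relapse or serious transplant complication | None |
| Severe pulmonary infection | None |
| Non-compliance or severe illness | None |
| Pregnancy | None |
| Own choice | None |

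**What 10.1 then does with the uncovered subjects.**

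- Progressive disease at entry: a responder if FEV1 is within 10% of baseline or better. Being on CIS is not required.
- Stable disease at entry: a responder with an FEV1 increase of 10% or more. Being on CIS is not required.
- Stable disease at entry with stable FEV1: a responder only with a 25% immunosuppressant reduction during CIS treatment. This route is tied to the drug.

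**Late intolerance.** Under 4.0 this subject goes off study and is a non-responder by 10.3. Under 10.5.2 the same subject is off study drug only and is scored on FEV1. The two sections give different scores.

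**Reproducing the design.** Inputs from 10.2: the null rate "is 0.3 or less against the alternative hypothesis"; the alternative that the response proportion ("improvement or stabilization) is 0.5 or more"); and "With alpha = 0.05and 80% power, a maximum of 39 subjects will be needed for each of study groups A and B". Stage 1 continues with 7 or more of 19; success needs 17 or more of 39. The exact success probability is

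P(success | p) = Σ over x = 7 to 19 of Bin(x; 19, p) × P(Y ≥ 17 − x), with Y ~ Bin(20, p).

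This gives 0.0455 at p = 0.30 and 0.804 at p = 0.50. A search for the smallest maximum sample size returns the same 6/19, 16/39 design, so the plan's figure is confirmed.

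**Illustration.** Let the rate be 0.30 when off-drug subjects count as non-responders. Let f be the share of analysed subjects who stop CIS, are not failed by 10.2, and stay for assessment. Let q be the share of those who meet the FEV1 criteria. The scored rate is 0.30 + f × q.

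Both f and q are assumptions. The documents give no discontinuation rate, and f is taken as 5–10%. For q the range is 10–60%, the span Section 2.5 gives for improvement or stabilization on existing treatment.

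| f | q | Scored rate | Extra responders in 39 (39 × f × q) | P(17 or more of 39) |
|---|---|---|---|---|
| 0 | – | 0.300 | 0 | 0.046 |
| 5% | 10% | 0.305 | 0.2 | 0.053 |
| 10% | 10% | 0.310 | 0.4 | 0.060 |
| 5% | 60% | 0.330 | 1.2 | 0.101 |
| 10% | 60% | 0.360 | 2.3 | 0.189 |

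**The confidence-interval rule.** Section 10.2 also tests the null through the lower limit of a 95% interval. The exact two-sided lower limit is 0.278 for 17 of 39 and 0.301 for 18 of 39, so 18 responders would be needed. Under that rule the chance of success at 0.30 is 0.023. It becomes 0.027 and 0.032 at q = 10%, and 0.057 and 0.119 at q = 60% (f = 5% and 10%).

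**The case against.** The strongest reply is that the plan already fails the subjects who matter most. A reader might infer from 10.3 that leaving the study is the only route to non-response, or that 4.0 and 10.5.2 score progressing subjects differently. Neither follows. Section 10.2 fails progression and post-week-9 escalation for BOS whether the subject is off study or only off drug. The conflict between 4.0 and 10.5.2 changes the score only for late intolerance.

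A reader might also picture a subject stabilised on new BOS treatment being credited to CIS. That case is mostly closed: new or increased immunosuppression for BOS after week 9 is itself a failure, and 10.5.1 encourages withdrawers to keep attending only until they start alternative BO therapy. Increases for GVHD outside the lung, however, leave the subject on study under 6.2.3.

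The size is uncertain too. The rates in Section 2.5 come from patients treated for BO, often with more systemic immunosuppression, and do not describe the uncovered group. Some uncovered reasons, such as relapse with death expected or ECOG 3 or worse, make two stable PFTs at weeks 18 and 19 unlikely. This favours the lower part of the range.

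Finally, scoring retained subjects on observed FEV1 could be a deliberate treatment-policy choice, and it fits the inclusion of nearly all who begin treatment. The documents do not say so, and the wording of the first-stage rule points to response to the drug.

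These replies narrow the point. They do not supply a rule for the uncovered reasons.

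**Conclusion.** The gap is real but limited. For the stopping reasons marked None in the table, the plan as written lets a subject who is no longer taking CIS count as a responder: by stable FEV1 with progressive disease at entry, or by a 10% increase in any subject. For late intolerance, 4.0 and 10.5.2 lead to different scores.

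On the stated assumptions, the chance of reaching 17 of 39 at a true 30% goes from 4.6% to between about 5% and 19%. At the low end the effect is negligible; at the high end it is about two extra responders in 39. The direction is always towards success. The range depends wholly on f and q, which the documents do not give. The gap in the rules does not depend on them.

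**What to change.** In 10.2 and 10.3, state that any subject in the primary analysis set who permanently stops CIS before the week 18 assessment is a non-responder in the primary analysis, whether or not assessments continue. Add a sensitivity analysis that scores these subjects on observed FEV1. Say that permanent stopping does not include the temporary medication holds in 6.2.1. Word the sentence so that it leaves the stated handling of subjects unable to tolerate 150 mg for two weeks unchanged; 10.2 and 10.3 exclude and replace them.

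Reconcile the off-study wording in 4.0 with the off-study-drug wording in 10.5.2.

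If scoring by observed FEV1 is what was intended, the plan should say so and describe the endpoint accordingly.

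The cost is a few sentences. The 6/19, 16/39 design keeps its maximum of 39, exact alpha of 0.0455 and power of 0.804. The observed response rate may be slightly lower.
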